- 1. Change in patient reported outcome of face and hand skin symptoms from baseline to Day 28, of at least 2 points on a 0-10 point scale where 0 = none and 10 = worst.
 - a. pain
 - b. redness
 - c. dryness
 - d. cracking
 - e. roughness
 - f. itching
 - g. overall skin irritation

Secondary endpoints

- 1. Change from baseline to Day 28 in pH.
- 2. Change from baseline to Day 28 in TEWL.
- 3. Change in S. aureus colonization from baseline to Day 28.

Inclusion Criteria

- 1. HCW using PPE at least 6 hours/day, 4 days/week or, depending on shift work, 24 hours/week, for at least one (1) month,
- 2. Men or women, any age
- 3. Overall skin irritation score of at least 4 on 0-10 scale where 0 =none and 10 =worst
- 4. Must be willing to stop use of any other emollient and lotion for one (1) week between screening and baseline visit and for the duration of the study.
- 5. Participant is willing to stop use of, or not begin, use of any topical corticosteroids, emollients and lotions to the hands and face for the duration of the trial.

Exclusion Criteria

- 1. History of any skin disorder existing prior to March 1, 2020 characterized by chronic visible lesions or skin irritation symptoms including, but not limited to atopic dermatitis, eczema, moderate-severe acne, chronic dry skin and psoriasis.
- 2. Use of topical or systemic corticosteroids within one (1) month of baseline visit.
- 3. History of any significant medical condition that, in the opinion of the investigator, might put the subject at risk in this trial.
- 4. Participation in another clinical trial within 30 days or 5 half-lives of the study agent, whichever is longer.

Study test item

EpiCeram® 90 gram tubes

Number Subjects

Fifty (50) subjects will be evaluated in this study. Accordingly, 55 subjects will be enrolled to allow for a 10% drop out rate.

Efficacy Measurements

- 1. Symptom scales
 - a. pain
 - b. redness
 - c. dryness
 - d. cracking
 - e. roughness
 - f. itching
 - g. overall skin irritation
- 2. Surface Skin pH
- 3. TEWL
- 4. SCH
- 5. Antimicrobial peptides (LL-37, HBD-2)
- 6. Free fatty acids
- 7. Bacterial qPCR
 - a. S. aureus
 - b. MRSA
 - c. S. epidermidis

Safety Measurements

Adverse Events

Statistics

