21.0 Statistical considerations

Descriptive statistics will be calculated for all demographic and clinical characteristics at baseline and study outcomes for each time period. Means and standard deviations will be

presented for continuous variables (e.g. age) or proportions and frequencies for categorical variables (e.g., sex) to describe the sample.

Paired t-tests will be used to assess differences in the primary outcomes of face and hand skin irritation symptoms (pain, redness, dryness, cracking, roughness, itching and overall skin irritation) between the baseline visit and Day 28 follow-up visit. The same analysis will be conducted for the secondary outcomes of pH, TEWL, and S. aureus colonization level. All statistical tests for the primary outcomes will be conducted will be two-tailed with α set at 0.05. All *p*-values will be reported with high precision (to the 4th decimal place) so that multiple comparisons adjustments may be applied, as desired. Table 1 below shows how the results will be presented.

The analysis will be performed on the Intention-to-Treat sample. If there is attrition over the course of the study, attritors will be compared to completers in terms of measures taken at baseline. Any significant differences will be reported.

All variables will be checked for outliers and skewness by visually examining boxplots. Further evaluation of any outliers identified through visual checks will be conducted to assess if any participants should be excluded from the analysis. The assumptions for each inferential statistical test will be evaluated. In the event assumptions are not met, results from a Wilcoxon signed rank test will also be reported.

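### Section 21.0 gives the S. aureus qPCR endpoint no scale, non-detect rule or deciding test, and its outlier rule puts high-load carriers at risk of removal

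*Combined protocol and SAP*

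**What the plan says.** Section 21.0 sets the primary analysis, "Paired t-tests will be used to assess differences in the primary outcomes of face and hand skin irritation symptoms", comparing baseline with Day 28, and extends it: "The same analysis will be conducted for the secondary outcomes of pH, TEWL, and S. aureus colonization level". The Statistics part of the Synopsis also lists S. aureus under the paired t-test and mentions no fallback. The Synopsis states the endpoint as "Change in S. aureus colonization from baseline to Day 28"; Section 5 words it as a reduction. Section 3 shows that the measurement is a qPCR result from one palm swab of the dominant hand at each of two visits.

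No section gives a unit, a scale, a detection limit or a rule for undetected samples. The separate collection manual is not among the documents. It may state the assay limit, but the analysis scale belongs in Section 21.0.

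Section 21.0 handles assumptions in three steps:
- The screen is visual and covers every outcome: "All variables will be checked for outliers and skewness by visually examining boxplots".
- Removal of subjects may follow from that screen: "Further evaluation of any outliers identified through visual checks will be conducted to assess if any participants should be excluded from the analysis". No criterion is given, and the same section places the analysis on the Intention-to-Treat sample.
- A second test is added where needed: "In the event assumptions are not met, results from a Wilcoxon signed rank test will also be reported". Which of the two results governs is not stated.

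Sections 6.1 and 6.2 do not make S. aureus carriage a condition of entry. On numbers, "Fifty (50) subjects will be evaluated in this study".

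**The concern.** Bacterial load by qPCR commonly spreads over orders of magnitude. Because carriage is not required for entry, some subjects can be expected to be undetected at both visits. On an untransformed scale a few heavy carriers then dominate both the mean change and its standard error, and a paired t-test can be weak against a fall that is large in proportional terms.

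The plan leaves three choices until the data are in hand: the scale, the test that counts, and who is excluded as an outlier. In an open-label study these choices would be made with results visible. This endpoint is the only listed secondary endpoint that addresses Objective 3 (S. aureus load), and it bears on hypothesis d in Section 2. The subjects most exposed to exclusion are those who carry the information about a reduction.

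**Working it through.** **1. The plan's own figure.** The Synopsis states 80% power for n = 50, d = 0.4, two-sided α = 0.05. By the normal approximation, 0.4 × √50 = 2.828; 2.828 − 1.960 = 0.868; Φ(0.868) = 0.807. The noncentral t gives 0.792. The figure is reproduced, but nothing in the plan links d = 0.4 to any reduction in S. aureus.

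**2. What a 10-fold fall means as a standardised effect.** Assumptions: every subject is a carrier, log10 load is normal, with between-subject SD *sb* and independent visit-level SD *sw*.
- Log10 scale: d = 1 / (√2 × *sw*).
- Raw scale: with A = exp[5.302(*sb*² + *sw*²)], B = exp[5.302 *sb*²] and 5.302 = (ln 10)², d = 0.9 / √(1.01A − 0.2B − 0.81).

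| *sb*/*sw* | A | B | d, raw | d, log10 |
|---|---|---|---|---|
| 1.0/0.6 | 1354 | 200.7 | 0.025 | 1.18 |
| 0.7/0.4 | 31.4 | 13.4 | 0.17 | 1.77 |
| 0.5/0.3 | 6.07 | 3.76 | 0.42 | 2.36 |

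The same biological fall is far below the planned d = 0.4 on the raw scale at wide spread, and about equal to it at narrow spread. Raw differences are too skewed for the normal formula to turn these values into power, so power was simulated.

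**3. Simulated power.** Inputs: n = 50 from the plan; all others are assumptions. Carriers' mean log10 load is 3.5, carriers fall by 1.0 log10, non-carriers are undetected at both visits, and carriage is 20-70%. Ranges run over carriage.

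| *sb*/*sw* | Raw paired t | log10 paired t |
|---|---|---|
| 1.0/0.6 | 7-36% | 82-100% |
| 0.7/0.4 | 28-79% | 95-100% |
| 0.5/0.3 | 55-96% | 98-100% |

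The log10 test was at least as powerful as the raw test in every cell. Wilcoxon on the untransformed differences gave 73-100% at 1.0/0.6. The lower end for log10 depends on non-detects. With 3% sporadic detection in non-carriers and undetected values set to half a limit of 1 log10, it is 62% at 1.0/0.6, with Wilcoxon at 70%. For a fall of 0.5 log10 (about 3-fold) at 1.0/0.6, power was 3-14% raw, 29-92% log10 and 28-79% Wilcoxon.

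**4. A second model.** Mean log10 load is 3 at baseline and 2 at Day 28, with one SD for log10 load, visit correlation 0 to 0.8, and non-carriers at zero. At SD 1.0:

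| Carriers | Raw t | log10 t | Wilcoxon |
|---|---|---|---|
| 100% | 0.49-0.66 | 1.00 | 0.99-1.00 |
| 50% | 0.25-0.46 | 0.92-1.00 | 0.83-1.00 |
| 30% | 0.13-0.26 | 0.69-1.00 | 0.61-0.97 |
| 20% | 0.07-0.15 | 0.46-0.94 | 0.40-0.89 |

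At SD 0.5 the raw t-test had power from 0.59 (20% carriers) to over 0.99 (all carriers).

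**5. Conflict between the two planned tests.** In the model of step 3 at 1.0/0.6, Wilcoxon was significant and the raw t-test was not in 64-77% of simulated trials. At narrow spread this cannot happen often: with raw power of 96%, at most 100 − 96 = 4% of trials can show it.

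**6. The boxplot screen.** If fewer than 25% carry S. aureus, the upper quartile equals the undetected value, the box has zero height, and every detected value is flagged. With the usual 1.5 × IQR rule on raw baseline values at 1.0/0.6, about 8-11 of 50 subjects were flagged per trial. At 20% carriage about 93% of detected subjects were flagged.

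**The case against.** A reader might infer that a true 10-fold fall would usually be missed and Objective 3 reported as showing no effect. The documents do not support that, for three reasons.
- The plan does not choose the raw scale; it is silent. The low power figures describe one permitted reading.
- No SD, carriage rate or target reduction is given. At log10 SDs of 0.5/0.3 even the raw t-test detects the fall in 55-96% of trials.
- Section 21.0 requires a skewness check and, if assumptions fail, a Wilcoxon result. Data skewed enough to defeat the t-test should trigger it, and it keeps most of the power. The fall would usually appear in the report, next to a t-test that disagrees.

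Other objections also have force. Flagged subjects are to be evaluated further, not removed automatically. The zero-height box would occur on the log10 scale too, so discretionary exclusion is a separate weakness from the choice of scale. With few carriers and wide spread every test is limited (0.46 for log10 and 0.40 for Wilcoxon at 20% carriers, SD 1.0, correlation 0). Half the detection limit is only one defensible convention. This is one of three secondary endpoints in an uncontrolled study, and no stated decision turns on its p-value.

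What none of this answers is that the scale, the non-detect rule and the deciding test are left open, and that exclusion has no criterion.

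**Conclusion.** The point holds as a gap in prespecification with a measurable cost. The paired t-test is the named analysis, its scale is unstated, the Wilcoxon test is an addition with no rule of precedence, and boxplot outliers may be excluded at discretion.

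If the untransformed scale is used, power for a 10-fold fall drops from 82-100% to 7-36% at SDs 1.0/0.6, from 95-100% to 28-79% at 0.7/0.4, and from 98-100% to 55-96% at 0.5/0.3. The direction is stable across the inputs tried. The size rests on assumed SDs, carriage and load. Under wide spread the expected consequence is a pair of conflicting p-values that the plan cannot resolve. The change should be made, in proportion to a secondary endpoint.

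**What to change.** In Section 21.0, with the Synopsis aligned:
- Define the S. aureus outcome as change from baseline to Day 28 in log10 qPCR load, and state the unit and detection limit.
- Fix the value for undetected samples in advance, for example half the detection limit.
- Name one deciding test: the paired t-test on log10 change or the signed-rank test. Label the other as supportive if it is kept.
- State that no participant is excluded from this endpoint on the basis of boxplot outliers.
- Tabulate detected and undetected at each visit, descriptively.

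The cost is wording only, with no new data or visits. The effect would be reported as a fold change, not as an absolute difference in load.

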Descriptive statistics will be calculated for all demographic and clinical characteristics at baseline and study outcomes for each time period. Means and standard deviations will be presented for continuous variables (e.g., age) and proportions and frequencies for categorical

variables (e.g., sex). Paired t-tests will be used to assess unadjusted differences in primary outcomes of face and hand skin irritation symptoms (pain, redness, dryness, cracking, roughness, itching and overall skin irritation) and secondary outcomes of pH, TEWL, and S. aureus colonization level between the baseline visit and Day 28 follow-up visit. Analysis will be performed on the Intention-to-Treat (ITT) sample. Standard data quality checks will be performed. The sample size of n = 50 is sufficiently powered $(1 - \beta = 0.80)$ to identify a medium effect size of d = 0.4 in a two-tailed test with α set at 0.05. Given the multiple primary endpoints, *p*-values will be reported with high precision (four percentage points) to allow for multiple comparisons adjustments as desired.

EpiCeram for skin protection in healthcare workers using personal protective equipment.

Protocol #: PPE-01

1. Introduction:

During the current COVID-19 pandemic, health care workers (HCW) report that the prolonged use of personal protective equipment (PPE), particularly gloves and face covering, results in irritant contact dermatitis manifested by symptoms of pain, itching, burning and non-specific discomfort of the hands and face and associated visible physical changes of erythema, dryness, roughening and cracking of the affected skin (Jiang, et al 2020). These changes are aggravated by frequent hand washing and antimicrobial alcohol use. These irritative changes are likely associated with defects in the normal barrier structure and function of the skin, including, but not limited to, lowering of pH, excessive water loss, alteration of skin microbiome, lowered resistance to allergens and pathogens and immunological dysfunction. It is unknown whether these changes could increase the likelihood of S. aureus skin contamination or, in people exposed to, but not systemically ill with, COVID-19 to act as "silent" carriers of coronavirus.

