EpiCeram, a marketed product, is a three lipid emollient that has been shown to improve barrier structure and function, reduce skin pH, helps restore the microbiome components toward normal, improve immunological function and reduce symptoms associated with disrupted skin surfaces (Elias 2014, Elias 2019 and Kircik 2014). In contrast, some readily available over the counter skin care products may actually increase barrier dysfunction and aggravate skin disease (Li 2017, Elias 2019).

2. Hypotheses

- a. The signs and symptoms of skin irritation secondary to extensive use of PPE will be accompanied by measurable defects in skin barrier structure and function.
- b. EpiCeram will improve measurements of skin barrier integrity.
- c. Signs and symptoms of skin irritation will improve after one month of EpiCeram use.
- d. Improvement of skin barrier function will restore reduce skin colonization by pathogenic bacteria.

3. Study design

This will be a one (1) month, open label study. Subjects must be HCW who have used face and hand PPE at least four (4) days a week for a minimum of one (1) month (or, depending on shift work, at least 24 hours/week) and who have new (after March 1, 2020) symptomatic skin irritation on the hands and/or face. No change to required hand washing protocols or other protective measures will be required.

At Visit 1, Screening the study will be explained and an informed consent document (ICD) signed. Subjects will be entered into the electronic data capture (EDC) system using a direct data capture (DDC) tablet. Subjects will complete an overall skin irritation assessment on 0-10 scale where 0 = none and 10 = worst. If it is equal to or greater than 4, the subject may proceed to

enrollment provided all other inclusion and exclusion are met. If the subject has not used any lotions and emollients for the previous one (1) week on the face and hands, washout is not necessary, and Baseline visit activities may be performed at the Screening visit. Subjects requiring washout, will refrain from using any lotions and emollients for one (1) week between Visits 1 and 2 and then, for the duration of the study. Visit 2 (Baseline) will occur seven (7) days after Visit 1.

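### Seven primary symptom scales are each tested at two-sided 0.05 with adjustment left open: if none truly changes, the chance of at least one false improvement is about 16% to 6% (assumed correlation 0 to 0.9), against 2.5% for one test

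*Combined protocol and SAP*

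**What the plan says.** Section 21.0 compares baseline with Day 28 by paired t-test on seven primary outcomes: overall irritation and six specific symptoms (itching, pain, cracking, dryness, redness, roughness). The level is set per test: "All statistical tests for the primary outcomes will be conducted will be two-tailed with α set at 0.05". P-values go to the fourth decimal "so that multiple comparisons adjustments may be applied, as desired". If test assumptions fail, "results from a Wilcoxon signed rank test will also be reported".

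The Synopsis (Statistics) recognises the issue and leaves it open in the same way: "Given the multiple primary endpoints", p-values are given precisely "to allow for multiple comparisons adjustments as desired". It describes n = 50 as having 80% power "to identify a medium effect size of d = 0.4 in a two-tailed test with α set at 0.05".

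The endpoint definitions differ from this analysis:
- **Synopsis, Primary Endpoint:** a change of at least 2 points, followed by the seven scales, with no count.
- **Section 4a:** a change of at least 2 points in overall irritation.
- **Section 4b:** a change of at least 2 points in any two of seven items, with overall irritation appearing again as item 7.

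The hypothesis is directional (Section 2, c): "Signs and symptoms of skin irritation will improve after one month of EpiCeram use".

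**The concern.** The sponsor identified several primary endpoints and then deferred the decision on them until the p-values are known. No section names an adjustment method, a testing order, or the number of significant scales that would make the study positive. The same seven p-values could therefore be presented as success or failure, and either presentation would fit the text.

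Only improvement supports the product, so the relevant error is a significant decrease on a scale with no true change. One test carries 2.5% in that direction; seven carry more. Any adjustment made to control this lowers the power for each symptom below the stated 80%.

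The endpoint wording does not close the gap. The count in Section 4b refers to symptoms that change by 2 points, not to significant tests, and Section 21 does not analyse it.

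**Working it through.** **Inputs from the documents.** Seven tests, two-sided 0.05 each (Section 21.0), so 0.025 in the improvement direction; n = 50, d = 0.4, power 0.80 (Synopsis, Statistics).

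**Assumptions.** One score per symptom, normally distributed changes, and a common correlation ρ between scales of 0 to 0.9. The documents give no correlation. One subject rates all seven scales at the same visit, so ρ = 0 is an extreme.

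**1. The plan's own figure.** n = ((1.960 + 0.842)/0.4)² = 49.06, rounded up to 50. With the exact noncentral t (49 df, noncentrality 0.4 × √50 = 2.83), power is 0.792. The sample size reproduces for one unadjusted test.

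**2. Independent scales, no true change.**
- At least one false improvement: 1 − 0.975⁷ = 0.162.
- At least two: 1 − 0.975⁷ − 7 × 0.025 × 0.975⁶ = 0.012.
- At least one significant in either direction: 1 − 0.95⁷ = 0.302, against 0.05.

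**3. Correlated scales, no true change.** Given a shared normal factor u, each scale is falsely significant with probability p(u) = 1 − Φ((1.96 − √ρ·u)/√(1−ρ)). Averaging P(Bin(7, p(u)) ≥ j) over u gives:

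| ρ | 0 | 0.3 | 0.5 | 0.7 | 0.8 | 0.9 |
|---|---|---|---|---|---|---|
| At least one | 16.2% | 13.7% | 11.5% | 8.9% | 7.4% | 5.7% |
| At least two | 1.2% | 2.9% | 3.7% | 4.0% | 4.0% | 3.7% |
| All seven | <0.001% | 0.001% | 0.02% | 0.13% | 0.30% | 0.68% |

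Simulated t-tests at n = 50 (40,000 trials per ρ) agree: 16.1% falling to 5.8% for at least one, 1.2% to 4.0% for at least two, at most 0.65% for all seven. At ρ = 0.95, at least one falls to 4.6% and all seven rises to 1.1%.

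**4. Some scales truly improve.** Suppose the true effects are large enough to be significant almost always.
- One true improvement: a false second arises from the other six with probability 1 − 0.975⁶ = 14.1% at ρ = 0, falling to 5.4% at ρ = 0.9.
- Six true improvements: an all-seven claim is false whenever the last scale is significant by chance, about 2.5%.

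The second and third rows of the table are therefore full-null figures, not maxima.

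**5. Holm's procedure.** Simulation of the full null (100,000 trials per ρ) gives a false-improvement rate of 2.4% (ρ = 0) falling to 1.0% (ρ = 0.9).

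Per-symptom power at d = 0.4, n = 50:
- Unadjusted: 0.79.
- Bonferroni level, 0.05/7 = 0.00714: 0.51 (80% would need d = 0.52).
- Holm, all seven scales at d = 0.4: 0.63 to 0.60 on average.

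**6. Endpoint against test.** The t-test asks whether the mean change differs from zero. With an assumed change SD of 2 to 4 points (not in the documents), it is significant from 2.01 × SD/√50 = 0.57 to 1.14 points. It does not test a 2-point threshold, and the documents do not say whether the 2 points apply to each subject or to the group mean.

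**The case against.** **The plan is transparent.** Precise p-values are promised for every test, so any reader can apply Holm or Bonferroni. That mitigates the problem, but it does not fix in advance what the sponsor will claim.

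**The stated alpha and power are per-test figures.** This stands. A reader might infer that the plan's 0.05 and 80% are wrong. They are not: Section 21.0 sets a level for the tests and claims no familywise level, and the Synopsis states power for a single test. What is missing is the allowance for seven.

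**The success rules are mine.** Also true. No section defines an overall success claim, and a reader might take Section 4b as a rule requiring two significant tests. It counts 2-point changes and is not linked to the t-tests.

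**Some rules look harmless.** A reader might take 1% to 4% for two scales, or under 1% for all seven, as upper limits. Step 4 shows they are not.

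**Regression to the mean may matter more.** The study is open-label and single-arm, and entry requires overall irritation of at least 4 (Section 6.1c). That scale can improve with an inert product, and no multiplicity rule corrects this. The point stands and belongs beside the main analysis.

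**Two inferences to avoid.** Section 21.0 says "Table 1 below shows how the results will be presented", but that table is not in the text available, so nothing is concluded from its absence. Nor do the documents say that face and hand are scored separately, so fourteen tests cannot be assumed.

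**Conclusion.** The concern holds as an unspecified multiplicity rule combined with primary endpoints that do not match the planned analysis. Followed as written, the plan allows at least one false improvement in about 16% to 6% of trials, roughly 6 to 2 times the 2.5% for one test. This assumes no true mean change on any scale and a common correlation of 0 to 0.9. The sample size is correct for what it describes, one unadjusted test.

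These figures concern mean before-after change only. Even a fully adjusted result would not show that the product caused the improvement. The point should be fixed before outcome data are seen; it does not invalidate the study.

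**What to change.** Before outcome data are seen:

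1. **Multiplicity (Synopsis Statistics and Section 21.0).** Replace the open-ended adjustment with a commitment: the seven primary paired t-test p-values are tested by Holm's procedure at familywise two-sided 0.05. Improvement is claimed only for symptoms with a Holm-adjusted p below 0.05 and a mean decrease. Unadjusted p-values are still shown, and any Wilcoxon results are supportive. Holm is one valid choice among several; what matters is committing to one.
2. **Power (Synopsis).** State that 80% refers to one unadjusted test. Add that per-symptom power at d = 0.4 and n = 50 is about 51% at the Bonferroni level, or about 60% to 63% on average with Holm if all seven scales have d = 0.4.
3. **Endpoints (Synopsis Primary Endpoint and Statistics, Sections 4 and 21.0).** Make them agree. Name mean change as the primary analysis and remove the second listing of overall irritation from 4b. Report the 2-point and any-two criteria as subject-level proportions with 95% confidence intervals, labelled supportive (for example, 25 of 50 gives 37% to 63% by Wilson's method).
4. **Interpretation (Section 21.0).** State that the study is single-arm and that overall irritation is the entry variable. Regression to the mean can therefore produce improvement that Holm does not correct, and adjusted significance shows before-after change, not a product effect.

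**Cost.** A protocol amendment under Section 16.3, because Section 4 changes. No added subjects, visits or measurements. Fewer individual symptoms may be claimable.

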6.1 Inclusion Criteria

- a. HCW using PPE at least 6 hours/day, 4 days/week or, depending on shift work, 24 hours/week, for at least one (1) month
- b. Men or women, any age
- c. Overall skin irritation score of at least 4 on 0-10 scale where 0 = none and 10 = worst
- d. Willing to stop use of any other emollient and lotion for one (1) week between screening and baseline visit and for the duration of the study.
- e. Participant is willing to stop use of or not begin use of any topical corticosteroids, emollients and lotions to the hands and face for the duration of the trial.

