6.2 Exclusion Criteria

a. History of any skin disorder existing prior to March 1, 2020 characterized by chronic visible lesions or skin irritation symptoms including, but not limited to

atopic dermatitis, eczema, moderate-severe acne, chronic dry skin and psoriasis.

- b. Use of topical corticosteroids within one (1) month of baseline visit.
- c. History of any significant medical condition that, in the opinion of the investigator, might put the subject at risk in this trial.
- d. Participation in another clinical trial within 30 days or 5 half-lives of the study agent, whichever is longer.

7. Test Item and Proscribed Treatments

This is an open label study. All subjects will receive EpiCeram, delivered in 90 gm tubes. The EpiCeram cream will be applied to face and hands at least three (3) times per day, about every 8 hours taking care to apply after bathing and before applying any makeup. Subjects are prohibited from using any other skin lotion by prescription or over the counter. Subjects are specifically prohibited from using any corticosteroid containing skin products.

8. Number of Subjects

Fifty (50) subjects will be evaluated in this study. To account for subjects who fail to complete the trial fifty-five (55) subject will be enrolled.

9. Safety measurements Adverse events

10. Efficacy measurements

- a. Symptom scales
- b. TEWL
- c. Hydration
- d. Skin pH
- e. Skin surface bacterial qPCR

11. Study Procedures

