13.0 Early Termination Visit Procedures

If a subject wishes to end his/her participation in the study prematurely, whether because of an AE or any other reason, he/she should be asked to complete a termination visit at the next scheduled appointment or within 14 days, whichever is more convenient. The investigator should make every reasonable attempt to perform the final assessment. Whenever possible, all final visit procedures should be performed at the time of an early termination visit. All outstanding AEs should be followed to resolution or stability. The reason for early termination should be clearly stated in the source and data collection tool.

All adverse events that result in a subject's withdrawal from the study must be reported to the Project Manager of Clinical Investigation, [name], BSN [contact] cell), within 24 hours.

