16.5 Source Documents

FDA regulations (21 CFR 312.62b) require an investigator "to prepare and maintain adequate and accurate case histories that record all the data and other observations pertinent to the investigation on each individual" participating in a clinical investigation whether or not they were administered the investigational product. "Case histories include the case report forms and supporting data including, for example, progress note of the physician, the individual's hospital charts, and nurses' notes. The case history for each individual shall document that informed consent was obtained prior to participation in the study." Source documents may be reviewed and compared with data collection tool/CRFs at all monitoring visits. All source documents and data collection tool/CRFs should be complete and up to date and filed in chronological order in the subject's study file.

The investigative site must maintain logs for the following:

- a. Screening visits
- b. Randomization
- c. Study product dispensed and returned
- d. Monitor visits
- e. Study personnel
- f. Telephone contact

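### Section 21 promises an Intention-to-Treat analysis but lets participants be excluded after boxplot review, without limiting this to confirmed errors or requiring the result with everyone retained

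*Combined protocol and SAP*

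**What the plan says.** Section 21.0 (Statistical considerations) fixes the population: "The analysis will be performed on the Intention-to-Treat sample". The Statistics part of the Synopsis agrees: "Analysis will be performed on the Intention-to-Treat (ITT) sample".

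The next paragraph of Section 21.0 sets the data check: "All variables will be checked for outliers and skewness by visually examining boxplots". It continues: "Further evaluation of any outliers identified through visual checks will be conducted to assess if any participants should be excluded from the analysis". The unit that may be removed is the participant, not the value. No numerical threshold, ground for exclusion, decision-maker or timing is given. The same paragraph adds a Wilcoxon signed rank test when the assumptions of a test fail.

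Section 7 describes the design: "This is an open label study. All subjects will receive EpiCeram, delivered in 90 gm tubes". The primary outcomes are self-reported 0–10 scores, compared between baseline and Day 28 by paired t-test, two-tailed at 0.05.

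**The concern.** An ITT analysis keeps participants whatever their outcome. A rule that allows removal after the outcomes have been seen works against that, unless it is confined to values shown to be wrong. On a 0–10 self-report scale, a subject who worsens or improves sharply may be a perfectly valid result.

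Two things are at stake. First, removing valid extremes shrinks the standard deviation of the changes, so the paired t-test can reject more often than its stated 5%. Second, the result would still be labelled ITT. With one open-label arm, and the outcome data in view when exclusion is considered, a reader could not rule out selective removal. If only confirmed errors are removed, neither harm arises.

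**Working it through.** **1. The plan's own figure.** Inputs from the Synopsis (Statistics): d = 0.4, two-tailed α = 0.05, power 0.80, n = 50. For a paired test, n = ((1.960 + 0.8416)/0.4)² = 7.004² = 49.06, rounded up to 50. The noncentral t gives power 0.792 at n = 50. The sample size reproduces, and n = 50 is used below.

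**2. Does any other text supply the missing limits?**

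- Synopsis, Statistics: routine data quality checks are mentioned without content.
- Section 21.0, Wilcoxon test: triggered by failed test assumptions, not by exclusions. Nothing says it uses the sample before exclusions.
- Section 16.5: "Source documents may be reviewed and compared with data collection tool/CRFs at all monitoring visits". This allows source comparison but does not tie exclusion to its outcome.

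None of these limits exclusion to errors or requires the result with everyone retained.

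**3. Error rate if valid flagged participants are removed.** The statistic is t = mean change / (SD of change / √n). A participant is flagged below Q1 − 1.5 IQR or above Q3 + 1.5 IQR, where IQR is the interquartile range. The fence is an assumption, because the plan states none. Also assumed: integer 0–10 scores, baseline mean 6, SD 2 or 2.5, baseline–Day 28 correlation r of 0.3 to 0.7, no true change and all values valid. There were 40,000 trials per setting, with Monte Carlo standard error √(0.05 × 0.95/40,000) ≈ 0.001. The table gives two-sided error (%) over two independent runs with every flag removed.

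| SD, r | Flags on baseline or Day 28 | Flags on change |
|---|---|---|
| 2, 0.3 | 5.9–6.0 | 6.7–6.9 |
| 2, 0.5 | 5.5–5.6 | 6.5–6.8 |
| 2, 0.7 | 5.3–5.5 | 9.0–9.1 |
| 2.5, 0.3 | 6.1–6.4 | 6.9–7.2 |
| 2.5, 0.5 | 5.8–6.0 | 7.2–7.3 |
| 2.5, 0.7 | 5.4–5.5 | 7.4 |

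- All data kept: 4.7–5.1%.
- Continuous normal data, every flag removed: 5.6–6.7% (baseline or Day 28) and 7.3–7.6% (change).
- A random half of the flags removed: 5.1–5.6% and 5.8–6.9%.

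**4. The 9% cell.** With SD 2 and r = 0.7, the IQR of integer change scores sometimes collapses, and the fence then flags many ordinary subjects. If removal is applied only in trials with 5 or fewer flags, the error in this cell falls to about 5.7%. The same cap hardly alters SD 2.5, r = 0.5 (7.0% to 6.9%). The range to carry forward for change scores is therefore about 6.5–7.5%.

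**5. Effect size.** With a true 2-point improvement, the estimated improvement shifts as follows:

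- every change-score flag removed: +0.002 to +0.021 points;
- every baseline or Day 28 flag removed: +0.022 to +0.048;
- only unfavourable change-score flags removed: +0.023 to +0.054;
- only favourable ones removed: −0.022 to −0.035.

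**6. How often the step is reached.** On one scale, at least one subject is flagged in about 23–42% of trials. This is the chance of review, not of exclusion.

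**The case against.** The strongest reply is that the plan only asks for further evaluation and does not say that anyone will be removed. Removing every flag is an assumed extreme, and so is the fence. This stands: the figures are what the wording allows under assumptions, not a forecast. It does not answer the gap, because the wording does not stop at errors.

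A second reply is that little changes at the effect of interest. At a true 2-point improvement the test rejects in at least 99.5% of trials with or without removal. This also stands, and it keeps the point modest.

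A third is that the Wilcoxon test already protects against outliers. It does reduce their influence, but it is tied to failed assumptions and does not guarantee that every participant is retained.

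A reader might go further and infer any of the following.

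- *That the true error is 9–10%.* The 9% comes from the integer-fence behaviour in step 4. A figure of 10.1%, seen when the entry score of at least 4 (Section 6.1) is applied, uses the same fence on integer change scores and should not be relied on.
- *That it could be larger still.* Heavy-tailed changes gave 8.5–9.0%, and one strongly skewed shape gave about 40%. The documents give no distribution of change that would support either.
- *That the result will be biased toward benefit.* Dropping only outlying worsening would raise favourable false positives from a nominal 2.5% to 3.6–4.7%. Nothing in the documents says removal would be one-sided.

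**Conclusion.** The point holds as a gap between the ITT label and the exclusion rule in Section 21.0. The plan permits whole participants to be removed after their data are viewed, does not limit this to confirmed errors, and does not ask for the result with all retained.

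Under the assumptions in step 3, the two-sided error could rise from 5% to about 5.3–6.4% (baseline and Day 28 scores plotted) or about 6.5–7.5% (change scores plotted), and less with partial removal. These figures describe integer symptom scales and normal data. They are not estimates for TEWL, pH or *S. aureus* level, whose distributions the documents do not give.

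The estimated mean is barely affected. The cost lies in the error rate and in the credibility of the ITT label. The plan should be amended, but the documents do not show that any valid participant will be excluded.

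**What to change.** Replace the exclusion sentence in Section 21.0 with:

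> Boxplots trigger data queries only. A value confirmed as a recording, device or laboratory error, on documented grounds that do not depend on its effect on the result, is corrected or, if it cannot be corrected, set to missing for that variable only. All other values are retained, and no participant is excluded from the primary ITT analysis because of an outlying value. Any analysis without outliers is shown beside it as a sensitivity analysis.

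Mere agreement with source should not be the test: a faulty TEWL, pH or qPCR reading that was transcribed correctly would match its source and still be wrong.

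The cost is small. No added subjects, visits or measurements are needed, and n = 50 is unaffected. Section 16.5 words source comparison as an option, so some query work is added. In the simulations, keeping all valid values made the 95% interval about 3–4% wider than removing every change-score flag, and no more than about 1% wider than removing every baseline or Day 28 flag. The estimate may also look slightly less favourable.
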